4.2 Inclusion criteria

- Postoperative hemoglobin is between 5-7 mmol / L after a terme (>37 weeks) primary Caesarean section

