4.4 Sample size calculation

This study will examine whether intravenous iron gives an improvement of the hemoglobin content 3 weeks postoperatively in patients with a hemoglobin between 5-7 mmol / L after caesarean sections, compared with giving oral iron, as well as placebo.

Based on the assumption that a minimum of 0,5 mmol/L difference in the hemoglobin level is thought to be of clinical importance and a standard deviation of 0,7 mmol/L (based on a retrospective analysis and a comparable study ⁴) it was determined that, with an alpha of 5% and a power of 80%, for each group 32 patients are needed. For 3 groups this means 96 patients. Allowing for patients lost to follow-up, the study number was set on 120 patients to guarantee adequate numbers of patients in each group.

A retrospective analysis performed at the Maastricht University Medical Centre between 1 January 2015 and June 30 2015, showed that 66 patients had a primary caesarean section. If we exclude the patients that had an operation on Friday (because during the weekends the study-medication cannot be prepared) the remaining number were 46 patients. Of these 46 patients, 31 people had a hemoglobin level between 5.0 and 7.0 mmol / L. If we assume that 70% of patients want to participate in the study, this will lead to 44 patients per year to randomize at the MUMC⁺. The other participating hospital (Zuyderland Sittard-Heerlen) has a double amount of deliveries including Caesarean sections which means that we need at maximum 1,5 year to complete the study.

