7.2 Randomization, blinding and treatment allocation

Randomisation is performed by the ALEA Screening and Enrollment Application Software of Formsmvision BV (Abcoude). Minimisation with stratification factor Hemoglobin (5.0-6.0 or 6.1-7.0), age (<60 years or >=60 years), ASA (1-2 or 3-5), type of surgery (laprotomic, laproscopic or vaginal and other) and amount of blood loss (<500 mL or >=500 mL) will be performed. The minimization method supported by ALEA is based on the minimization principles published in a paper by Pocock & Simon²³.

With the kit-number the pharmacy knows which package the patient should receive. It will be ensured that the infusion line and the flask with NaCl or Ferinject[®] will be packed. Also the venflon will be covered by a gauze. The placebo capsules will exactly resemble the capsulated ferrous fumarate tablets.

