7.3 Study procedures

Interventions

Blood

Postoperative determination of the hemoglobin level is part of the regular care and will be performed on the first day after the operation.

In this study we want to examine the blood three times more than in the regular care, namely 1 day and 3 and 6 weeks postoperatively. At 1 day (after randomization and before treatment) it will be taken in the hospital. At 3 weeks the research nurse will visit the patient at home. At 6 weeks the patient will visit the hospital for the regular follow up.

Determination of other parameters in the blood will not lead to more discomfort of the patient.

The lab results will be saved using an anonymous survey number.

Administration of an infusion

Each patient has postoperative IV, so no extra IV is needed for the study. The patient will receive either a flask NaCl (placebo) or a single dose of Ferinject[®] on the first or second day after the operation (24-48 hours postoperatively).

Capsules

The patient will start using capsules (either a placebo or ferrous fumarate) on the first or second day after the operation (24-48 hours postoperatively).

Each patient is given 60 capsules to take home, where she has to take 1 capsule 2 times a day.

Questionnaire

Each patient will be asked to complete a questionnaire four times: after informed consent before starting treatment, and 1, 3 and 6 weeks postoperatively. This questionnaire is a combination of the EuroHRQoL and MFI questionnaires. Completing the questionnaire takes about 10-20 minutes and can be filled in via computer or on paper.

This will be conducted as follows: the first questionnaire will be completed in the hospital the first day postoperatively before the study-medication is started. After 1 week the research nurse will call the patient at home to ask how things are going and whether the second questionnaire has been completed. After 3 weeks the nurse visits the patient and will ensure that the questionnaires about the quality of life after 1 and 3 weeks are completed. The day the patient will come for the regular check at 6 weeks, she will also be seen by the research nurse who will check whether the last questionnaire has also been completed.

Data collection

Patient characteristics. The following information will recorded:

- Age
- Morbidity

- Race
- ASA score
- Use of iron therapy preoperative (doses and duration of iron therapy)
- Amount of blood loss during surgery

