9. STATISTICAL ANALYSIS

9.1 Primary study parameter

Primary study parameter is change in hemoglobin level (mmol/L) between baseline and either 3 or 6 weeks postoperatively. Differences in change between the two experimental groups, and between each experimental group and the control group will be tested by use of the Student's T-test.

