9.2 Baseline differences

Differences in baseline characteristics are not expected in view of randomization. In order to check for any imbalances, values of variables measured at baseline (including hemoglobin) will be compared between groups (means for continuous variables, percentages for categorical variables). No statistical testing of baseline differences will be done since all differences will be due to chance.9.3 Multivariable analysis. In case of prognostically important baseline differences between groups, multivariable linear regression analysis will be carried out instead of the Student's T-test.

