9.3 Multivariable analysis

In case of prognostically important baseline differences between groups, multivariable linear regression analysis will be carried out instead of the Student's T-test.

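### The default t-test in 9.1 leaves out the factors on which 7.2 balances the arms; it is valid but possibly conservative, and pre-specified adjustment is a nearly free improvement

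*Combined protocol and SAP*

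**What the plan says.** - **Allocation (7.2).** "Minimisation with stratification factor Hemoglobin (5.0-6.0 or 6.1-7.0") is followed by "age (<60 years or >=60 years), ASA (1-2 or 3-5), type of surgery (laprotomic, laproscopic or vaginal and other") and by blood loss, split at 500 mL. The probability of assigning the favoured arm is not stated.
- **Primary test (9.1).** The outcome is change in hemoglobin from baseline. Differences between the two iron groups, and "between each experimental group and the control group will be tested by use of the Student's T-test". No covariates enter.
- **Baseline check (9.2).** "values of variables measured at baseline (including hemoglobin) will be compared between groups", descriptively and without significance tests.
- **Fallback (9.3).** "In case of prognostically important baseline differences between groups, multivariable linear regression analysis will be carried out instead of the Student's T-test". Neither a threshold nor a covariate list is given.
- **Size (4.4).** For a difference of 0.5 mmol/L and an SD of 0.7, "with an alpha of 5% and a power of 80%, for each group 32 patients are needed", giving 96, raised to 120 for losses.
- **Data.** Section 7.3 records the ASA score and "Amount of blood loss during surgery". Annex 1 has hemoglobin measured after surgery.

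**The concern.** Balancing a prognostic factor removes most of its contribution to the difference between arms. An unadjusted t-test still counts that factor's variance as noise, so its standard error is larger than the real sampling error of the difference. The test then rejects less often than 5% under the null, and the intervals are wider than they need be. The remedy in 9.3 depends on seeing an imbalance, yet minimisation exists to prevent imbalance in these very factors. The plan may therefore forgo precision from data it already collects, and it leaves the choice of primary model to a judgement made after the baseline data are seen.

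**Working it through.** **1. The plan's own figure.** By the normal formula, n = 2 × [0.7 × (1.960 + 0.842) / 0.5]² = 30.8, so 31 per arm. The exact noncentral t gives 79.0% power at 31 and 80.3% at 32, so 32 is reproduced. 96 / (1 - 0.20) = 120, or 40 per arm, where the t-test has 88.4% power.

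**2. Limiting case.** Let perfectly balanced factors explain a share R² of the outcome variance. R² is an assumption; the documents give none.
- True t-test alpha = 2 × [1 - Φ(1.96 / √(1 - R²))]. R² = 0 gives 5.0%; 0.1 gives 2 × [1 - Φ(2.066)] = 3.9%; 0.2 gives 2 × [1 - Φ(2.191)] = 2.8%.
- The adjusted SD is 0.7 × √(1 - R²). Adjusted power at 32 per arm with three covariates is 80.2%, 84.2% and 88.1%.

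**3. Simulated minimisation.** Minimisation is imperfect, so the allocation itself was simulated: three arms, 96 patients, 40,000 allocations with two outcome draws each, total SD held at 0.7, difference 0.5. Assumed, because the documents do not say: favoured-arm probability 0.8, low hemoglobin stratum 35%, blood loss ≥500 mL 50%, ASA 3-5 5%, and all prognostic effects. Patients were split 1:2 between hospitals, in line with the doubled delivery volume in 4.4. The regression included all three arms. Monte Carlo error is about 0.15 points on power and 0.1 on alpha.

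| Assumed effects, mmol/L (low Hb / blood loss / hospital) | Variance explained | t-test power | Adjusted power | Gain | t-test alpha |
|---|---|---|---|---|---|
| 0 / 0 / 0 | 0% | 80.3 | 79.9 | -0.4 | 5.0% |
| 0 / 0 / 0.2 | 1.8% | 80.3 | 80.6 | +0.3 | 4.9% |
| 0 / 0 / 0.3 | 4.1% | 80.3 | 81.5 | +1.2 | 5.1% |
| 0.3 / 0.2 / 0 | 6.2% | 80.9 | 82.3 | +1.3 | 4.4% |
| 0.3 / 0.2 / 0.3 | 10.3% | 80.8 | 83.8 | +3.1 | 4.4% |
| 0.5 / 0.3 / 0.2 | 18.0% | 81.7 | 86.9 | +5.2 | 3.5% |

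Gains are taken before rounding. Adjusted alpha was 4.9-5.1% throughout. In the last row the adjusted SD is 0.7 × √0.82 = 0.634, so the standard error of a difference falls from 0.7 × √(2/32) = 0.175 to about 0.158.

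**4. At 40 per arm.** For the first, fifth and sixth rows: 88.4 to 88.2 (-0.2), 89.0 to 91.3 (+2.3), 90.0 to 93.4 (+3.4). A second, smaller simulation (2,500 runs, so √(0.8 × 0.2 / 2500) = 0.8 points of error per power figure) assumed no, moderate and strong effects. It gave -0.6, +2.3 and +6.2 at 32 per arm and -0.8, +1.7 and +5.0 at 40. The direction is the same.

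**5. What is not covariate adjustment.** A three-arm model with no covariates already beats the pairwise t-test by pooling variance. The exact calculation gives 80.3 to 80.7, and simulation gave 81.4 to 81.9 and 81.8 to 82.2. So about 0.5 of any gain, and at most about 1, is pooling. By the same token, useless covariates cost more than the net -0.4: about 0.4 + 0.4 = 0.8 points, still under 1.

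**6. The 9.3 switch.** Suppose that an important difference meant any two arms differing by 10, 15 or 20 percentage points in low hemoglobin or blood loss. The switch would occur in 18%, 5% and 0.6% of trials, against 91%, 68% and 40% under simple randomisation. The 10-point figure moves from 1.4% to 38.2% as the favoured-arm probability goes from 1.0 to 0.7, and it is 71% at 0.8 if hospital is also checked. The threshold and the probability are both unstated, so the rate cannot be established. All that can be said is that minimisation lowers it for these factors.

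**The case against.** **The plan is valid as written.** This is correct. A t-test on change scores with a conditional regression is a legitimate choice, it errs on the safe side, and no section promises adjustment.

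**The size is assumed.** Also correct. Even the sign depends on prognostic strength. The 5-point end needs a hemoglobin-stratum effect of 0.5 mmol/L, as large as the treatment difference in 4.4. The relevant n is also nearer 40 than 32 per arm, because 7.5 keeps results of patients who drop out and 9.6 carries the last hemoglobin forward.

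**Change from baseline already uses baseline hemoglobin.** Only with a fixed coefficient of 1. If baseline is uniform over 5-7 (variance 4/12 = 0.333) and follow-up rises by 0.7 per unit of baseline, baseline explains 0.3² × 0.333 / 0.49 = 6% of the variance of change; at a slope of 0.5 it explains 0.5² × 0.333 / 0.49 = 17%. Both slopes are illustrative.

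**The fallback may well operate.** This stands in part. Section 9.2 compares means for continuous variables, and balancing two strata does not fix mean hemoglobin. Race, morbidity or preoperative iron use could also prompt regression. A reader might infer that the switch would almost never happen; the documents do not support that.

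**The factor list in 7.2.** Eligibility is "Postoperative hemoglobin is between 5-7 mmol / L after a terme (>37 weeks) primary Caesarean section", so the age split at 60 and the type of surgery are in effect constant, and hospital is absent although two recruit. A reader might infer that the randomisation must be repaired. Adding hospital to the minimisation changed t-test power by less than 1 point in every row above, so this is only an observation.

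**Conclusion.** The mismatch between 7.2 and 9.1 is real and minor. A reader might infer bias, an inflated false-positive rate or an underpowered trial. None follows: the t-test kept its stated 80% power in every scenario, and its alpha stayed at or below 5% within simulation error. What is lost is efficiency, and only if the balanced factors predict the change in hemoglobin. In that case true alpha is about 3.5-4.5% under the assumed effects and the intervals are too wide.

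Adjustment is worth about -0.5 to about +5 power points at 32 per arm. At 40 per arm it is worth -0.2 to +3.4 in the main simulation and -0.8 to +5.0 in the smaller one. About 0.5-1 point of any gain is variance pooling. These ranges rest wholly on assumed effects, prevalences and minimisation probability; stronger effects would give more, and none would give a loss of under 1 point.

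**What to change.** - **9.1:** make the default primary comparison a linear regression of change in hemoglobin on arm, postoperative hemoglobin (continuous), blood loss (<500 or ≥500 mL), ASA (1-2 or 3-5) and hospital. Keep the t-test as a sensitivity analysis.
- **9.3:** do not make adjustment for these factors conditional on an observed imbalance.
- **7.2:** leave unchanged.

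Both text changes should be made before unblinding. The coding of hospital should be written down, because sections 3, 4.1 and 4.4 name the second site differently. No new data are needed. The cost is under 1 power point if no covariate predicts the outcome. ASA accounts for 0.1-0.3 of that if ASA 3-5 is as rare as the assumed 5%; it is kept because it is a minimisation factor.

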9.2 Baseline differences

Differences in baseline characteristics are not expected in view of randomization. In order to check for any imbalances, values of variables measured at baseline (including hemoglobin) will be compared between groups (means for continuous variables, percentages for categorical variables). No statistical testing of baseline differences will be done since all differences will be due to chance.9.3 Multivariable analysis. In case of prognostically important baseline differences between groups, multivariable linear regression analysis will be carried out instead of the Student's T-test.

9.3 Multivariable analysis

In case of prognostically important baseline differences between groups, multivariable linear regression analysis will be carried out instead of the Student's T-test.

9.4 Secondary study parameters

Quality of life

Each patient will be asked to complete three questionnaires at four times: at baseline after informed consent before starting iron treatment, and 1, 3 and 6 weeks postoperatively. The questionnaires are: 1) the EuroQoL, a generic health related quality of life questionnaire. In this questionnaire patients indicate their current health in five dimensions: mobility, self-care, usual activities, pain/discomfort, and anxiety/depression 2) the Multi-Dimensional Fatigue Questionnaire which is a 20-item self-reported instrument to measure fatigue. At baseline (first day postoperatively in the hospital but before the study-medication is started) patients will be asked to complete the questionnaires. At 1 week after start of the treatment, the research nurse will call the patient at home to ask whether the second questionnaire has been completed. After 3 weeks the nurse visits the patient and will ensure that the questionnaires about the quality of life after 1 and 3 weeks are completed. At 6 weeks, the patient will visit the outpatient clinic and will also be seen by the research nurse who will check whether the last questionnaire has also been completed.

Quality of life data between the groups will be analysed using Repeated Measurement

ANOVA.

Side effects of the medication

The next side effects will be registered: headache, constipation, diarrhea, nausea, dizziness, rash and stomach-ache. On questionnaire B, C, and D the patients can indicate whether there is any of these side effects.

For each potential side effect, the percentage of patients reporting it will be compared between groups. Groups will be compared using the Chi-square test.

Predictive value of other parameters

We will determine for number of parameters whether they predict patients' sensitivity to iron supplementation. These parameters are: CRP, transferrin, ferritin and hepcidin. The significance of these parameters will be determined by doing subgroup analyses among patients with either high or low values of the parameters (i.e. the similar analyses as in 9.1 but within subgroups).

Cost-analysis

Resource use and costs of the intravenous and oral iron therapy will be measured. If relevant and appropriate, a cost-minimisation or a cost-effectiveness analysis will be performed. In that case, the analysis will include a time-horizon of 6 weeks and be performed from a health care perspective.

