7.5 Replacement of subjects in case of withdrawal

A dropout of 10-20% is taken into account. Results will still be included, unless the patient withdraws consent. Assessments that will be done at the withdrawal visit are adverse events, drug accountability and collect not-used study medication.

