8.2 Aes, SAEs and SUSARs

8.2.1 Adverse events (AE)

Adverse events are defined as any undesirable experience occurring to a subject during the study, whether or not considered related to the investigational product. All adverse events reported spontaneously by the subject or observed by the investigator or his staff will be recorded

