Annex 1. Assessment schedule

Visits and Timepoints ¹	Pre-operative	Surgery	Post-operative	Week 1	Week 3	Week 6	Withdrawal
	Screening			Telephone call	Home visit		
Assessments	Day - 3 to -1	Day 0	Day 1, within 24-48 hours after surgery	Day 7	Day 21	Day 42	
Informed consent	X						
Inclusion/exclusion criteria	X						
Demography (age, race)	X ²						
Relevant Medical History / Current medical conditions	X ²						
ASA score	X ²						
Type of surgery		X ²					
Amount of blood loss during surgery		X ²					
Hb	X		X		X	X	
Transferrin, Ferritin, CRP	X		X ²		X	X	
Hepcidin	X		X ²		X	X	
QoL questionnaires			X ²	X	X	X	
(Serious) Adverse events			X ²	X	X	X	X
Randomization			X ²				
Dispense studymedication			X ²				
Drug accountability			X ²		X	X	X
Collect not-used study medication						X	X
¹ Due to logistic reasons adjustments in timepoints can occur							
² Only if post-operative Hb is within 5 and 7 mmol/L

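### The planned side-effect comparison draws on questionnaires B, C and D, and the withdrawal visit has none, so a side effect that makes a woman leave before her next questionnaire is not counted

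*Combined protocol and SAP*

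**What the plan says.** Section 9.4 fixes the items: "The next side effects will be registered: headache, constipation, diarrhea, nausea, dizziness, rash and stomach-ache". It names where they come from: "On questionnaire B, C, and D the patients can indicate whether there is any of these side effects". It then defines the comparison: "For each potential side effect, the percentage of patients reporting it will be compared between groups", and "Groups will be compared using the Chi-square test". It gives no denominator.

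The letters B, C and D are not defined. Section 7.3 gives the timing: "Each patient will be asked to complete a questionnaire four times: after informed consent before starting treatment, and 1, 3 and 6 weeks postoperatively". The first form is the baseline one, so B, C and D are most naturally weeks 1, 3 and 6.

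Section 7.5 lists what happens when a woman leaves: "Assessments that will be done at the withdrawal visit are adverse events, drug accountability and collect not-used study medication". Annex 1 agrees. Its row "QoL questionnaires" is marked post-operatively and at weeks 1, 3 and 6, with no mark under withdrawal. The adverse-event row is marked at those times and at withdrawal.

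Section 8.2.1 describes how adverse events are collected: "All adverse events reported spontaneously by the subject or observed by the investigator or his staff will be recorded". Section 8.3 sends them to the ethics committee with the annual report. Section 7.5 also says that the results of women who drop out are kept unless consent is withdrawn. Section 9.6 has missing-data rules for hemoglobin and baseline characteristics, but none for side effects.

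**The concern.** Whether the data are missing can depend on the outcome itself. A side effect bad enough to end participation also prevents the next questionnaire from being completed, and that questionnaire is the only named source for the comparison. Milder complaints in women who stay are counted, while the complaint that drove a woman out is not.

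Comparing side effects between the drugs is a secondary objective (section 2), and the introduction says that the effect of iron will be weighed against its side effects. If withdrawal for intolerance differs between arms, the arm with more of it will look better tolerated than it was.

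**Working it through.** **1. No planned figure to reproduce.** The plan states no expected rate or power for the side-effect comparison. Its sample size concerns hemoglobin. The inputs used here are:
- 120 women in three groups (4.4). With equal allocation, which is assumed, that is 120/3 = 40 per arm.
- Dropout of 10-20% (7.5), so 0.10 × 40 = 4 to 0.20 × 40 = 8 women per arm, for all reasons.
- Ferrous fumarate: constipation 1-10%, diarrhea 0.1-1%. Ferinject: constipation and diarrhea both 1-10% (12.2).

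**2. Follow one woman through the plan.** She starts study medication 24-48 hours after surgery (7.3), develops a listed side effect, and leaves before her next form.
- Questionnaires: none is completed after the side effect begins, and none is scheduled at withdrawal (7.5, Annex 1).
- Adverse-event record: the event has a planned place there, at the withdrawal visit or as a spontaneous report.
- Comparison in 9.4: no sentence brings that record in, so she is not in the numerator.

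The same happens if she completes B without the complaint, develops it later and leaves before C. It does not happen if she stops the capsules but stays in the study, because she still receives the forms.

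**3. The exposed time.** If B is the week-1 form, the first exposed interval is about 5 to 6 days (day 1 or 2 to day 7). It can be longer. At week 1 the nurse only telephones to ask whether the form is done, and completion of the week-1 and week-3 forms is ensured only at the week-3 home visit (7.3).

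**4. Effect of one such woman.** Let x of 40 women in an arm have the side effect, and let one of them leave uncounted.
- Rate with her counted: x/40.
- Kept as a non-reporter: (x − 1)/40, lower by 1/40 = 2.5 points.
- Dropped from the denominator: (x − 1)/39, lower by x/40 − (x − 1)/39 = (40 − x)/1560.

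| x (assumed) | Counted | Kept as non-reporter | Dropped | Shift in points |
|---|---|---|---|---|
| 2 | 5.0% | 1/40 = 2.5% | 1/39 = 2.6% | 2.5 or 2.4 |
| 4 | 10.0% | 3/40 = 7.5% | 3/39 = 7.7% | 2.5 or 2.3 |
| 6 | 15.0% | 5/40 = 12.5% | 5/39 = 12.8% | 2.5 or 2.2 |
| 8 | 20.0% | 7/40 = 17.5% | 7/39 = 17.9% | 2.5 or 2.1 |

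The shift is about 2 to 2.5 points per woman on either reading of the denominator. The counts x are assumptions. For constipation, the 1-10% band corresponds to 0.4 to 4 women of 40, so the first two rows fit the protocol's own figures better than the last two.

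**The case against.** The strongest reply is that the plan does not say the questionnaires are the only source. Section 9.4 says that the side effects will be registered and that patients can indicate them on the forms. Section 7.5 keeps the results of women who leave, and the withdrawal visit assesses adverse events. Read together, these passages allow an analyst to include the withdrawal record. That stands as far as it goes: the exclusion is inferred from silence, and the event is not lost to the trial. But permission is not a rule. An analyst who follows 9.4 as written uses B, C and D and has no instruction to add anything.

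Four stronger conclusions are tempting but are not supported.
- *She leaves both numerator and denominator.* Section 9.4 gives no denominator, and 7.5 points if anything towards keeping her. Only her absence from the numerator is common to both readings.
- *Oral iron is the arm that benefits.* Section 6.3 says that its gastrointestinal effects are dose dependent, but it compares no withdrawal rates. Section 12.2 puts constipation in the same band for both drugs and diarrhea in a higher band for Ferinject.
- *About half the rate is lost.* This needs, for example, 3 of 6 affected women to leave uncounted: 3/37 = 8.1% or 3/40 = 7.5%, against 6/40 = 15.0%. Three early leavers for one complaint would be 3/8 = 38% to 3/4 = 75% of an arm's whole expected dropout, and a constipation rate of 15.0% exceeds the protocol's own 1-10%.
- *A real difference would be missed.* That too depends on assumed counts. The comparison is secondary, and the plan gives no power for it.

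**Conclusion.** The point holds in a limited form. Applied as written, section 9.4 does not count a listed side effect that makes a woman leave before her next questionnaire, although the event should be in the adverse-event record. The rate can be understated in whichever arm has more such withdrawals. The documents do not identify that arm, and the total effect is unknown.

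The size per woman rests on 40 per arm. The conclusion also assumes that B, C and D are the post-baseline forms and that no source outside 9.4 is meant to feed the comparison. A woman who withdraws consent is a separate case, because 7.5 does not promise to keep her results. The matter deserves correction because the omission depends on the outcome being measured and because the visit needed to close it is already planned.

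**What to change.** - **Collection (7.5, Annex 1):** add the seven-item side-effect list to the withdrawal visit.
- **Source (9.4):** define B, C and D by week, and count the withdrawal list together with them. For women who withdraw without completing the list, count a listed side effect recorded as an adverse event up to withdrawal. Do not add adverse-event records for women who stay, since that would mix solicited and spontaneous reports throughout.
- **Denominator (9.4):** all randomised women who started study medication and have any post-baseline side-effect information, from a questionnaire or a withdrawal assessment. A woman whose adverse-event record is counted in the numerator belongs in the denominator too. Report by arm the number with no information; counting them as event-free would itself understate the rates.
- **Reporting:** tabulate withdrawals due to side effects by arm, and show the questionnaire-only result alongside.

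The cost is a few sentences in 9.4 and seven tick-boxes at a visit that already assesses adverse events. The downside is that two kinds of report are combined for the few women who withdraw. The questionnaire-only result shows how much that matters.

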The patient will have 3 extra blood tests to determine hemoglobin, CRP, ferritin and transferrin. In addition, 4 times the patient has to fill in a questionnaire about the quality of life. One time, fluid will be administered to the patient; this may be sodium chloride 0.9% or Ferinject[®]. The needle for the infusion does not have to be inserted another time as this has already been done before every operation. In addition, the patient must take capsules for one month (ferrous fumarate vs. placebo). Not treating a patient (the group that gets an oral and intravenous placebo) will not entail significant risks, but may cause a longer time of fatigue and dizziness. Literature also shows that not treating a patient with a hemoglobin around 5 mmol/L is justified. The group treated with oral or intravenous iron preparations may have gastrointestinal side effects or skin reactions. No serious adverse events have been described. The occurrence of a serious allergic reaction to Ferinject[®] is extremely rare.

The advantage of treating a patient may be that the hemoglobin level during the first 6 weeks normalizes more rapidly, which may affect the quality of life during the first 6 weeks postoperatively.

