9.5 Alpha

We will employ an alpha of 5% (2-sided testing).

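### The seven solicited side-effect items have no pre-treatment answer, so where background symptoms are common and persist, the percentages are not drug rates and the comparison between arms loses precision

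*Combined protocol and SAP*

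**What the plan says.** Section 7.3 plans four questionnaires: one before treatment, then at weeks 1, 3 and 6. On the first it says that "the first questionnaire will be completed in the hospital the first day postoperatively before the study-medication is started". The only content it names is the EuroQoL-type instrument and the fatigue inventory.

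Section 9.4, under side effects of the medication, lists seven symptoms: rash, headache, dizziness, nausea, stomach-ache, constipation and diarrhea. It places them as follows: "On questionnaire B, C, and D the patients can indicate whether there is any of these side effects". The analysis is a chi-square test on the percentage of patients reporting each item. There is no condition that a symptom be new, worse than before treatment, or judged related to treatment.

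The Summary says that leaving a patient untreated "will not entail significant risks, but may cause a longer time of fatigue and dizziness". Section 12.2 says much the same. Dizziness is one of the seven items.

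**The concern.** Treatment starts 24 to 48 hours after a caesarean section in women with hemoglobin of 5 to 7 mmol/L. Some of the seven symptoms may already be present then, and by the protocol's own account dizziness is also a symptom of the anemia. Without a day-1 answer, a symptom carried over from surgery or anemia cannot be told from one that began after dosing.

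Two things are at stake. First, the introduction says that the effect of iron will be weighed against its side effects, and a percentage that includes carried-over symptoms overstates what the drug causes. Second, symptoms shared by all arms shrink the absolute difference and add variance, so a real excess is harder to see.

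**Working it through.** **The plan's own figure.** Section 4.4 takes "a minimum of 0,5 mmol/L difference in the hemoglobin level is thought to be of clinical importance", "a standard deviation of 0,7 mmol/L", and concludes "with an alpha of 5% and a power of 80%, for each group 32 patients are needed". The normal approximation gives n = 2 × (1.96 + 0.84)² × 0.7² / 0.5² = 30.7, so 31. The exact t calculation gives 32 (power 80.3%). Then 3 × 32 = 96, and 96 / 0.80 = 120, which matches "the study number was set on 120 patients". These figures reproduce, but they concern hemoglobin only. The documents give no rate or power for side effects.

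**Inputs for the side-effect check.**
- From the documents: 120 / 3 = 40 per arm (equal allocation assumed, as no ratio is stated); two-sided alpha 5% (section 9.5).
- Assumed: share b with the symptom on day 1; share s of those in whom it persists to follow-up; new-onset rates e0 on placebo and e1 on iron, which also apply to women whose day-1 symptom resolved. One iron arm is compared with placebo.

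**Formula.** The proportion reporting the symptom after treatment is p = b[1 − (1 − s)(1 − e)] + (1 − b)e = e + bs(1 − e). The difference between arms is therefore (e1 − e0)(1 − bs), so carried-over symptoms shrink it by the factor 1 − bs.

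**Worked case: b = 30%, s = 70%, e = 5% versus 30%.** Here bs = 0.21.
- Placebo: 0.05 + 0.21 × 0.95 = 0.2495. Iron: 0.30 + 0.21 × 0.70 = 0.447.
- Difference: 0.25 × 0.79 = 0.1975.
- The placebo arm shows 25% although the new-onset rate is 5%.
- Pooled p = 0.348. The critical difference is 1.96 × √(2 × 0.348 × 0.652 / 40) = 0.209. The standard error under the alternative is √((0.2495 × 0.7505 + 0.447 × 0.553) / 40) = 0.104. Power = Φ((0.1975 − 0.209) / 0.104), about 46%.

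**Same case with s = 5%.** Here bs = 0.015 and the difference is 0.25 × 0.985 = 0.246, so there is almost no dilution.

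**Power by simulation** (20,000 runs per scenario, reproducible to about one point). The adjusted analysis is a linear model with arm and day-1 answer.

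| Day-1 prevalence | Persistence | New onset | Any report, unadjusted | Any report, adjusted | New symptoms only |
|---|---|---|---|---|---|
| 20% | 70% | 5% v 30% | 57% | 72% | 80% |
| 30% | 70% | 5% v 30% | 46% | 63% | 74% |
| 40% | 70% | 5% v 30% | 38% | 53% | 67% |
| 30% | 5% | 5% v 30% | 85% | 85% | 74% |
| 30% | 70% | 5% v 15% | 12% | 17% | about 23–24% |

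The new-symptom rate is (1 − b)e, which is 0.035 versus 0.21 at b = 30% and does not depend on s. That is why its power stays at 74% while that of any report moves from 46% to 85%.

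**At the documents' drug rates.** Section 12.2 puts the Ferinject items at 1–10%, so 5% versus 15% is the top of that range. With no carried-over symptoms at all, power for that contrast is only about 35%. Section 7.5 expects 10–20% dropout, leaving 40 × 0.9 = 36 to 40 × 0.8 = 32 per arm, so all these figures are on the high side.

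**Type I error.** With 40 per arm and a common rate of 5%, 10%, 30% or 50%, the exact error of the two-arm test is 4.3%, 5.9%, 4.8% and 5.7%. The missing baseline does not inflate it in any material way.

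**The case against.** A reader might infer that background symptoms are being attributed to the drug, or that every difference is diluted. The documents support neither reading. The analysis compares groups, one of them a blinded double-placebo arm, so shared background does not create a false drug effect. An item with little background, such as rash (an assumption), is hardly affected, because 1 − bs is then close to 1.

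A reader might also want symptoms new since day 1 to become the main comparison. That holds only if day-1 symptoms mostly persist. At 5% persistence it has 74% power against 85% for any report, because it discards drug-caused symptoms in women who also had the symptom on day 1. The documents do not say which case applies. Adjustment is safer: in these scenarios it costs at most about 2 points of power and gains up to about 17.

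The text leaves some doubt. Letters A to D are undefined, and section 9.4 announces three questionnaires at all four times but names two, so the absence of the items from the first form is a strong inference, not a stated fact. Annex 1 also marks adverse events in the day-1 column. However, section 8.2.1 defines these as spontaneous or observed reports, and the schedule does not say that they precede dosing. That is partial cover, not a solicited baseline.

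Two limits stand in full. A day-1 item cannot separate drug-related dizziness from slower recovery of anemia, since that difference arises after randomisation. And at the documents' drug rates, small numbers limit these comparisons more than the missing baseline does.

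**Conclusion.** The point holds as a modest, inexpensive improvement to a secondary outcome. As written, the plan describes no solicited pre-treatment status for the seven items. The comparison with placebo remains valid and the primary analysis is untouched. For items with common, persisting background symptoms, the percentages by arm are not drug rates and precision is lost. In the illustration, adjustment moves power from 46% to 63% at 70% persistence and leaves it at 85% at 5% persistence.

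The size rests on assumed prevalence, persistence and onset rates. The contrast of 5% versus 30% exceeds the rates that the documents give. At 5% versus 15% the gain is from 12% to 17%, so these comparisons have low power with or without the change.

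**What to change.** - In sections 7.3 and 9.4, define questionnaires A, B, C and D by time point and content, and reconcile the count of three questionnaires with the two named.
- Add the same seven items to the questionnaire completed on day 1 before study medication.
- In section 9.4, keep all reported symptoms as the main comparison, but adjust or stratify it for the day-1 answer. Show symptoms new since day 1 in a supportive table.
- State that the side-effect comparisons have low power.

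The cost is seven tick-boxes on a form already in use, about a minute more per patient, and a short edit to the analysis text. The pre-treatment answer cannot be recovered after dosing, so the change helps only patients not yet treated.
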